To determine the sensitivity of the RS device for measuring change in fruit and vegetable (F&V) consumption in response to community-based nutrition interventions, we need to determine the longitudinal response to a defined F&V intervention. We want to learn if change in RS-measured skin carotenoids can be used to sensitively define F&V consumption changes across a range of consumption values. We would also like to determine if the RS device sensitivity differs by racial/ethnic group. Aim 2 will gauge what an increase in F&V intake would look like in terms of RS-assessed skin carotenoids in an ethnically and racially diverse population.

Study Setting

Participants will be recruited, enrolled, and measured from within the three intervention sites: 1) Greenville, North Carolina - East Carolina University (ECU), 2) Minneapolis, Minnesota - University of Minnesota (UMN), and 3) Houston, Texas - Baylor College of Medicine (BCM). At ECU, participant visits will take place at the East Carolina Diabetes and Obesity Institute facilities and the Department of Public Health Research (ECDOI) offices, located in the East Carolina Heart Institute. At UMN, participant visits will take place at the Epidemiology Clinical Research Center (ECRC) which is a part of the Division of Epidemiology and Community Health in the School of Public Health. At BCM, participant visits will take place at the Children's Nutrition Research Center Metabolic Research Unit (CNRC MRU).

Study Population, Eligibility, and Screening

Participants (n=160) will be recruited from the three intervention sites: ECU (n=60 participants), UMN (n=40 participants), and BCM (n=60 participants). As with Aim 1, participants will be recruited across four diverse groups: non-Hispanic African American/Black, Asian, non-Hispanic White, or Hispanic/Latinx. Though our power calculation found that a sample size of n=156 was needed, we chose to round up in order to easily and evenly divide participants by our three intervention sites. It is our intent to enroll approximately equal numbers of participants in each racial/ethnic group.

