3. Each pile will then be sealed in an envelope and sent to the appropriate intervention site.
4. Each site will receive four sealed envelopes (of randomized cards) – one for each race/ethnic group.

5. Once received at each site, study staff/data collectors should not open the envelopes until the first participant's visit.
6. At each participant's baseline study visit, data collectors will select the appropriate race/ethnic group envelope and will choose the card at the top of the pile.
7. The treatment group printed on the card will determine the participant's treatment group.
8. The participant's study ID should be written on the card once the treatment group is determined and kept within the participant's study folder.
9. It is important to keep track of each participant's assigned treatment group so that each participant receives the appropriate juice and instructions.
10. Note: Randomization for each participant will occur in the same way. The randomly assigned cards within each envelope should not be shuffled at any time after opening the envelope, and data collectors should always choose from the same place (e.g., top of the pile).

Data Collection and Study Visits

Over the course of the six-week trial, participants will complete three study visits at baseline, week 3, and week 6. During the baseline visit, participants will complete the informed consent process before beginning any study-related activities.

All data collection measures and methods outlined in Aim 1 will be repeated at all three Aim 2 study visits. These measures include height (baseline-only), weight and body fat percentage, 10-hour fasting blood draw, RS-assessed skin carotenoid measurements (via the Veggie Meter® device), skin melanin measurements (via the Konica Minolta CM-700d Spectrophotometer), and a food frequency questionnaire (the National Cancer Institute's web-based Diet History Questionnaire III (DHQ-III)). Demographic questions (such as birthdate, age, sex, and race) will be asked at baseline only. Demographic questions with the potential for responses that could change over the course of the study (such as education, marital status, and income) will be asked at all three time points (baseline, week 3, and week 6). Sun exposure and tobacco use questions will be asked at each visit as well to track any changes to these behaviors.

Blood collected at the study visit will be sent to three sites for analysis and storage:

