High-Dose V8 Orange Carrot Juice (12 fl. oz per day)	
• Provide participant with juice, instructions, pack of graduated cups, juice log/calendar (for weeks 1 – 3)• Study incentive (\$50)	
• Provide participant with juice and juice log/calendar (for weeks 4 – 6), additional cups if needed• Study incentive (\$100 at week 3 and \$150 at week 6)

Participant Incentive

All participants will receive \$300 across the 6-week study: \$50 at the baseline visit, \$100 at the week 3 visit, and \$150 upon completion of the final measures at week 6 visit. Participants at ECU and BCM will receive incentives through university issued Greenphire ClinCards. Participants at UMN will receive incentives as Target gift cards.

Intervention Adherence

One of the main challenges of the Aim 2 juice trial intervention is ensuring intervention adherence. To reduce risk of non-adherence, participants will be provided with an instruction sheet (see MOP Appendices) as well as a hard copy juice log (see MOP Appendices) on which we will ask them to mark the amount(s) of juice consumed each day. If all juice is not consumed, we will inquire why during the following study visit. Possible reasons include not liking the taste, spills, allergic reaction, someone else drinking the juice, and other. We will use this to measure dose and adjust for dose in our statistical analyses. Participants will also be reminded to maintain current diet and exercise habits. We will send all participants emails and allow them to opt in to receive text messages and/or phone calls (ensuring participant confidentiality) as periodic weekly reminders to drink the juice. The V8 Orange Carrot juice provides 60 kcal/6 fl. oz (or 120 kcal/12 fl. oz), and the control Mott's Apple Juice provides 90 kcal/6 fl. oz. We will provide an educational handout on the additional energy provided by the juices and dietary strategies to adjust caloric intake to remain isoenergetic.

Statistical Considerations

Power Calculation

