Aim 2 includes data from human subjects achieved by recruiting, enrolling, and collecting data from participants from North Carolina (East Carolina University, Greenville, NC), Minnesota (University of Minnesota, Minneapolis, MN), and Texas (Baylor College of Medicine, Houston, TX). Carotenoid analyses will occur at Eurofins Craft Technologies in Wilson, NC, and genetic analyses will occur at the USDA-ARS Children's Nutrition Research Center (CNRC) at Baylor College of Medicine in Houston, Texas. For Aim 2, we will conduct a 6-week randomized trial of a carotenoid-containing juice intervention among 156 racially and ethnically diverse participants in NC, MN, and TX. All study data will be stored in password-protected spreadsheets on password-protected computers and/or in locked filing cabinets.

Potential Risks

The primary risk for participants is risk of confidentiality breach. We will take all possible precautions to minimize this risk. Although there will be a link between a participant's data and their study-specific identification number, this link will be kept secure in password-protected computers available only to researchers directly involved in the study.

In addition, there is a risk of weight gain for Aim 2 participants who will be provided with Orange Carrot or apple juice. The Orange Carrot juice provides 60 kcal/6 fl. oz, and the apple juice provides 90 kcal/6 fl. oz. We will provide an educational handout on the additional energy provided by the juices and dietary strategies to adjust caloric intake as to remain isocaloric. If we see a >5% increase in body weight at the week 3 timepoint, staff will provide additional dietary education to the participant(s).

Upon study completion, we will share de-identified data with the scientific community, including investigators with appropriate credentials who wish to study relationships not proposed by investigators affiliated with the current project. The final dataset will not contain identifiers. However, to safeguard participants from potential breach of confidentiality/privacy, we will create a data-sharing agreement that ensures that 1) those with whom the data are shared will use it only for research purposes and will not identify any individual participant; 2) the data will be secured on password protected and appropriate computer technology; and 3) data will be destroyed or returned upon completion of data analysis.

Adequacy of Protection Against Risks

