We do not expect any AE as a result of participating in this study. However, if any AE occur study staff will report them using the AE section within the ECU IRB website. The Safety Officer will review and evaluate AE within 72 hours of being notified of the event by study staff. Any study-related SAE will be reported to NHLBI within the timeline set forth by the institute. A safety report containing AE, SAE, and their rates of occurrence will be generated every 6 months and reviewed by the Safety Officer at that time.

- Measurement and reporting of participant compliance to treatment protocol: Once participants who have been randomized to the intervention treatment group have started the juice intervention, compliance will be reviewed monthly by the Principal Investigator and Safety Officer. If compliance in the juice intervention becomes an issue, we will re-evaluate our compliance plan to improve compliance.
- There is a modest risk of weight gain for Aim 2 participants who will be provided with carotenoid-containing or apple juice. The juices provide 60 and 90 kcal/6 fl. oz, respectively. We will provide education on the additional energy provided and dietary strategies to adjust their caloric intake as to remain isocaloric. If we see a >5% increase in body weight at the week 3 timepoint, we will provide additional dietary education to the subjects.
- Measurement of retention status: For the Aim 2 juice intervention, we will collect measures similar to Aim 1 at baseline, 3 weeks, and 6 weeks after the participants are randomized to a control group (negligible-dose carotenoids), a moderate-dose carotenoids group, or a high-dose carotenoid group. Our goal is to retain at least 85% of our initial sample, though we have powered our study to accommodate a more conservative retention rate (80%). We will review the rate of subject accrual monthly during the initial enrollment period and dropout rates on a quarterly basis. We will make regular contact with participants to encourage continued participation.

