- Stopping rules: In this minimal risk study to determine the sensitivity of the RS device (the Veggie Meter®), it is very unlikely that an event would occur that would require stopping the trial. However, as previously described, we will monitor injury rates of all participants. The Safety Officer, together with the study investigators, will alert the IRB at East Carolina University and NHLBI if a larger than reasonably expected injury rate should occur among participants in the intervention condition.

COVID-19 Safety Plan

Research staff at each of the intervention sites will follow their home University's approved/required COVID-19 screening plan. Participant COVID-19 screening will occur via phone the evening before the participant's study visit and again upon arrival to the visit the following day. This process will occur at each of the three participant visits.

In addition to participant COVID-19 screening questions, each site has and will follow site-specific requirements for study/clinic/lab spaces. Common requirements across all three sites includes:

- Staff will be required to wear various levels of personal protective equipment (PPE) such as masks, gloves, and face masks
- Participants will be required to wear face masks
- Staff and participants should maintain a distance of 6 ft whenever possible during the study visit
- Staff will clean common surfaces (e.g., tables and chairs, pens/pencils/stylus, light switches, doorknobs/handles) and equipment (e.g., the Veggie Meter® device, the Konica Minolta device, scale/height board, TANITA scale, iPads/computers, computer mouse/touchpads) before and after each participant's visit.

References

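### The plan promises adverse-event rates but lists no adverse-event question at any visit, so the recorded rates would be undercounts that depend on juice adherence

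*Combined protocol and SAP*

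**What the plan says.** All references are to the combined protocol and SAP.

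- **Measurement and Reporting of Adverse Events.** The section opens with "We do not expect any AE as a result of participating in this study". Staff report any AE that does occur through the ECU IRB website, the Safety Officer reviews it within 72 hours of notification, and a report with AE and SAE rates is produced every six months. The same section names a modest risk of weight gain.
- **Stopping rules (same section).** Injury rates are monitored in everyone. The Safety Officer and investigators alert the IRB and NHLBI "if a larger than reasonably expected injury rate should occur" in the intervention condition. The Data and Safety Monitoring Plan glosses AEs as injuries, so the two sections concern the same count.
- **Data Collection and Study Visits.** "participants will complete three study visits at baseline, week 3, and week 6". "All data collection measures and methods outlined in Aim 1 will be repeated at all three Aim 2 study visits". The measures named there and in the timeline table include a 10-hour fasting blood draw at each visit. Neither list has an AE question.
- **Intervention Adherence.** "If all juice is not consumed, we will inquire why during the following study visit". Allergic reaction is one of the reasons foreseen.
- **Potential Risks.** "The primary risk for participants is risk of confidentiality breach". Weight gain is also listed; the blood draws are not.

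**The concern.** A rate is interpretable only if everyone in the denominator had a similar chance of having an event recorded. Here the numerator depends on participants volunteering an event, staff happening to see it, or juice having been left. Someone who drank every serving and had a reaction is never asked. Someone who left juice is asked why, and may then mention one.

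The six-monthly rates, and the injury-rate alert that draws on them, would therefore rest on an incomplete count whose completeness is tied to adherence. The 12 fl. oz arm has twice the daily volume to finish, so its participants may be asked more or less often than those in the two 6 fl. oz arms.

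**Working it through.** **1. The plan's own figures.** No AE rate, expected rate or draw total is stated, so there is none to reproduce. The enrolment behind the counts does reproduce. The power calculation needs 41 per group; with 20% attrition, 41 / 0.80 = 51.25, rounded up to 52, and 52 × 3 = 156. This is rounded up to 160 (60 + 40 + 60 by site): "Participants (n=160) will be recruited from the three intervention sites". Protection of Human Subjects keeps the lower figure: "among 156 racially and ethnically diverse participants in NC, MN, and TX". I use 160 as the maximum.

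**2. Visits and draws.**
- Fasting draws: 160 × 3 = 480 (156 × 3 = 468). If 20% leave before week 3, 160 + 2 × 128 = 416, where 128 = 0.80 × 160.
- Follow-up visits at which a question could be asked: 160 × 2 = 320 (156 × 2 = 312; 2 × 128 = 256 with 20% early loss).

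**3. How an event can reach the record.**

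| Route | Who is covered | What it depends on |
|---|---|---|
| Unprompted report | Anyone | The participant volunteering it |
| Staff observation | Those with an event during a visit | Timing |
| Inquiry about undrunk juice | Only those with juice left | Adherence |
| Weight measurement | Everyone | Detects weight change only |
| COVID-19 screening | Everyone, each visit | Question content not given |
| Illness before week 3 or week 6 | Those whose illness becomes known | Recording as an AE is not stated |
| 72-hour review, SAE reporting | Events already notified | One of the routes above |

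No row is a general AE inquiry made of everyone.

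**4. Direction of the error.** Let r be the true proportion with an AE and L the share of those participants with juice left. Let u be the chance that an event becomes known without the inquiry, and a the chance when the participant is asked why juice was left. I assume a ≥ u, since asking can only add. Then

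recorded proportion = r × [L·a + (1 − L)·u].

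- The result is below r unless the bracket equals 1.
- If nobody leaves juice (L = 0), it is r·u. If everyone does (L = 1), it is r·a. When a > u it rises with L, so completeness depends on adherence.
- Two arms with the same r, u and a but different L differ by r × (a − u) × (L₁ − L₂). This is zero if leftover juice is equally common in both.

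The documents give none of r, u, a or L. The formula supports a direction, not a number. If everyone is asked at each follow-up visit, with chance b of disclosure, the recorded proportion among attenders becomes r·b and L drops out.

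**5. What a follow-up question cannot reach.** The baseline and week 3 draws, at most 320 of 480, are followed by another visit. The week 6 draws, at most 160 of 480 or one third, are not.

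**6. Wording set side by side.** The general expectation of no AEs stands beside a weight-gain risk in the same section, an allergic reaction foreseen under Intervention Adherence, and three fasting draws per participant. Separately, the stopping rules monitor everyone but confine the alert to the intervention condition. That term is not defined for this three-arm design, in which every arm receives juice and has the draws.

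**The case against.** The plan describes a minimal-risk study and has other safeguards. The Data and Safety Monitoring Plan also promises prompt reporting of excessive AEs and of any SAE. The Safety Officer reviews each notified AE and can call for corrective action. Staff have repeated contact through weekly reminders, COVID-19 screening and weighing, and a faint at the draw would happen in front of them. The manual of procedures, which holds the participant forms, is not among the documents, so an AE item there cannot be ruled out. No comparison of AEs between arms is planned.

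All of this stands and limits the seriousness of the point. It does not fill the gap: the SAE and review routes still begin with notification, and none of the contacts is described as an AE inquiry.

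Three stronger readings are tempting and should not be drawn.
- **That the injury-rate alert is the only safety trigger.** It is not, as the reporting routes above show.
- **That the expected rate is fixed at zero, so the first bruise must raise an alert.** The opening sentence is a general expectation about AEs caused by participation, and provision for AEs follows at once. What counts as reasonably expected is left to judgement. The documents give no per-draw event rate, so any probability of crossing zero would rest on invented inputs.
- **That a false difference between arms will appear.** This needs leftover-juice and reporting rates that the documents do not give.

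Numerical alert limits by arm are likewise not something the documents show to be needed. Several limits checked repeatedly would bring false alerts of their own, and reliance on the Safety Officer's judgement is a defensible choice here.

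**Conclusion.** The point holds as a gap in ascertainment. Under the plan as written, AE rates would be undercounts whose completeness depends on adherence, and that dependence may differ between the 6 and 12 fl. oz arms. The size is unknown and cannot be derived from the documents.

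The conclusion rests on two assumptions: that some events are not volunteered unless asked about, and that the unavailable forms contain no routine AE question. If they do contain one, the protocol need only cite it. The planned analyses of skin and plasma carotenoids are unaffected. This is a low-cost improvement to safety reporting; it does not bear on the validity of the trial's main result. The two wording conflicts are secondary.

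**What to change.** **Main change.** Add one open, non-leading AE question at week 3 and week 6, put to every participant in all three arms whatever the juice log shows. List it among the visit measures and in the timeline table. State that the answers, together with spontaneous and staff-observed events, form the numerator of the safety-report rates, and show those rates by arm.

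**Wording.** Reconcile the expectation of no AEs with the weight-gain risk, the foreseen allergic reaction and the three fasting draws. Reconcile monitoring of everyone with an alert confined to the intervention condition, and define that term.

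**Cost.** At most 320 extra answers and a short protocol edit, with no change to treatment, endpoint or sample size. More minor events will be recorded. Effects of the week 6 draw that appear after the visit, and events in participants who leave before a visit, will still rely on spontaneous report.
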